Sponsor	JJVC, [name]
Clinical Phase	Development phase, Phase 2
Trial Registration	This study will be registered on ClinicalTrials.gov.
Test Article(s)	Investigational Products: JJV Investigational Multifocal Contact Lens manufactured in senofilcon A material. Approved Products: 1-Day Acuvue® Moist Brand Multifocal Contact Lens.
Wear and Replacement Schedules	
Wear Schedule: The Test and Control lenses are used as daily wear (note: the Test lens will be reusable and the Control lens daily disposable).
 
Replacement Schedule: The Test lens will be replaced at the optimization visit. The Control lens will be replaced after each day of wear as well as the optimization visit. The Test and Control lenses will also be replaced when lost or damaged

Objectives	
This primary objective of this pilot study is to evaluate the visual performance of the JJV Investigational senofilcon A Multifocal Contact Lens (Test) made using a new manufacturing process by comparison with 1-Day Acuvue® Moist Brand Multifocal (Control).
 
The secondary objective is to evaluate the clinical performance of the Test lens by comparisons with the control lens in the following areas:
 
 • Vision (subjective) • Comfort • Slit Lamp Findings • Patients' reported ocular symptoms
Study Endpoints	
Primary Endpoints: Binocular distance, intermediate and near visual performance under different lighting conditions.
 
Secondary Endpoints:
 
 • Overall quality of vision scores on CLUE scale • Overall comfort scores on CLUE scale • Subject reported ocular symptoms • Slit Lamp Findings

Clinical Study Protocol
Johnson & Johnson Vision Care, Inc.

Study Design	
This is a randomized-controlled, single-masked, crossover clinical trial. There are two study lenses. Each lens will be dispensed for 3 ± 1 days and then an optimization visit will occur. The final lens pair will be dispensed for 12 ± 2 days and the follow-up on the final lens pair will occur. The second study lenses will then be fit and the above sequence repeated.
 
See the flow chart at the end of the synopsis table for the schematic of the study visits and procedures of main observations (Figure 1).

Sample Size	Up to 48 subjects will be enrolled with a target completion of 40 subjects.
Study Duration	The study will last approximately 2-4 months.
Anticipated Study Population	Healthy male and female volunteers with presbyopia will be invited to participate in the study. Subjects will be adapted soft contact lens wearers in both eyes. Additional information regarding the eligibility of the population can be found in the inclusion/exclusion criteria outlined below.
Eligibility Criteria	
Potential subjects must satisfy all the following criteria to be enrolled in the study
 
Inclusion Criteria after Screening:
 
 1. The subject must read, understand, and sign the STATEMENT OF INFORMED CONSENT and receive a fully executed copy of the form. 2. The subject must appear able and willing to adhere to the instructions set forth in this clinical protocol. 3. The subject must be at least 40 years of age and not greater than 70 years of age at the time of consent. 4. Subjects must own a wearable pair of spectacles if required for their distance vision. 5. The subject must be an adapted soft contact lens wearer in both eyes (i.e. worn lenses a minimum of 2 days per week for at least 8 hours per wear day, for 1 month of more duration). 6. The subject must either already be wearing a presbyopic contact lens correction (e.g., reading spectacles over contact lenses, multifocal or monovision contact lenses, etc.) or if not respond positively to at least one symptom on the "Presbyopic Symptoms Questionnaire".

Clinical Study Protocol

Johnson & Johnson Vision Care, Inc.

	
Inclusion Criteria after Baseline:
 
7. The subject's distance spherical equivalent refraction must be in the range of +1.25 D to +3.75 D in each eye.8. The subject's refractive cylinder must be \leq0.75 D in each eye.9. The subject's ADD power must be in the range of +0.75 D to +2.50 D.10. The subject must have distance best corrected visual acuity of 20/20⁻³ or better in each eye. 
Potential subjects who meet any of the following criteria will be excluded from participating in the study:
 
Exclusion Criteria after Screening:
 
1. Currently pregnant or lactating.2. Any active or ongoing ocular or systemic allergies that may interfere with contact lens wear.3. Any active or ongoing systemic disease, autoimmune disease, or use of medication, which may interfere with contact lens wear. This may include, but not be limited to, diabetes, hyperthyroidism, Sjögren's syndrome, xerophthalmia, acne rosacea, Stevens-Johnson syndrome, and immunosuppressive diseases or any infectious diseases (e.g. hepatitis, tuberculosis).4. Any previous, or planned, ocular or intraocular surgery (e.g. radial keratotomy, PRK, LASIK, lid procedures, cataract surgery, retinal surgery, etc.).5. A history of amblyopia, strabismus or binocular vision abnormality.6. Use of any of the following medications within 1 week prior to enrollment: oral retinoid isotretinoin (e.g. Accutane), oral tetracyclines, oral phenothiazines, oral/topical/inhaled anticholinergics, systemic/topical corticosteroids.7. Use of any ocular medication, with the exception of rewetting drops.8. History of herpetic keratitis.9. History of irregular cornea.10. History of pathological dry eye.11. Participation in any contact lens or lens care product clinical trial within 30 days prior to study enrollment.12. Employee or immediate family member of an employee of clinical site (e.g., Investigator, Coordinator, Technician).
--	---

[figure not shown]
Clinical Study Protocol
Johnson & Johnson Vision Care, Inc.

	
13. Any known hypersensitivity or allergic reaction to Optifree®Replenish® multi-purpose care solution, sodium fluorescein or non-preserved rewetting drop solutions.
 
Exclusion Criteria after Baseline:
 
14. Clinically significant (Grade 2 or greater) corneal edema, corneal vascularization, corneal staining, tarsal abnormalities or bulbar injection, or any other corneal or ocular abnormalities which would contraindicate contact lens wear.
 
15. Entropion, ectropion, extrusions, chalazia, recurrent styes, glaucoma, history of recurrent corneal erosions.
 
16. Any current ocular infection or inflammation.
 
17. Any current ocular abnormality that may interfere with contact lens wear.

Disallowed Medications/Interventions	
Use of any prescription or over-the-counter (OTC) medications that may affect contact lens wear.
 
See section 9.1 for details regarding disallowed systemic medications.

Measurements and Procedures	See Section 7.2 for the detailed procedures.
Microbiology or Other Laboratory Testing	None
Study Termination	The occurrence of one or more Unanticipated Adverse Device Effect (UADE), or any SAE where relationship to study agent cannot be ruled out, will result in stopping further dispensing investigational product. In the event of a UADE or SAE, the Sponsor Medical Monitor may unmask the treatment regimen of subject(s) and may discuss this with the Principal Investigator before any further subjects are enrolled.
Ancillary Supplies/ Study-Specific Materials	Rewetting drops, lens cases, glass vials, saline, Early Treatment Diabetic Retinopathy Study (ETDRS) light cabinet, logMAR charts, and Near logMAR charts. Optifree®Replenish® Multipurpose Disinfecting Contact Solution.
Principal Investigator(s) and Study Institution(s)/Site(s)	A full list of Principal Investigators, clinical sites, and institutions is kept separately from the Study Protocol and is included in the study Trial Master File.

Clinical Study Protocol

Johnson & Johnson Vision Care, Inc.

Figure 1: Study Flowchart

Clinical Study Protocol

Johnson & Johnson Vision Care, Inc.

COMMONLY USED ABBREVIATIONS AND DEFINITIONS OF TERMS

ADD	Plus Power Required For Near Use
ADE	Adverse Device Effect
AE	Adverse Event/Adverse Experience
BCVA	Best Corrected Visual Acuity
BSCVA	Best Spectacle Corrected Visual Acuity
CFR	Code of Federal Regulations
CLUE	Contact Lens User Experience
COAS	Complete Ophthalmic Analysis System
COM	Clinical Operations Manager
CRA	Clinical Research Associate
CRF	Case Report Form
CRO	Contract Research Organization
CT	Center Thickness
D	Diopter
DMC	Data Monitoring Committee
eCRF	Electronic Case Report Form
EDC	Electronic Data Capture
ETDRS	Early Treatment Diabetic Retinopathy Study
FDA	Food and Drug Administration
GCP	Good Clinical Practice
HIPAA	Health Insurance Portability and Accountability Act
IB	Investigator's Brochure
ICF	Informed Consent Form
ICH	International Conference on Harmonization
IDE	Investigational Device Exemption
IEC	Independent Ethics Committee
IRB	Institutional Review Board
ISO	International Organization for Standardization
ITT	Intent-to-Treat
JJVC	Johnson & Johnson Vision Care, Inc.
LC	Limbus Center
LogMAR	Logarithm of Minimal Angle of Resolution
MedDRA [®]	Medical Dictionary for Regulatory Activities
MOP	Manual of Procedures
NIH	National Institutes of Health
OD	Right Eye
OHRP	Office for Human Research Protections
OHSR	Office for Human Subjects Research
OS	Left Eye
OU	Both Eyes
PD	Protocol Deviation
PHI	Protected Health Information
PI	Principal Investigator

Clinical Study Protocol
Johnson & Johnson Vision Care, Inc.

PIG	Patient Instruction Guide
PQC	Product Quality Complaint
PRO	Patient Reported Outcome
QA	Quality Assurance
QC	Quality Control
SAE	Serious Adverse Event/Serious Adverse Experience
SAP	Statistical Analysis Plan
SAS	Statistical Analysis System
SD	Standard Deviation
SOP	Standard Operating Procedure
UADE	Unanticipated Adverse Device Effect
USADE	Unanticipated Serious Adverse Device Effect
VA	Visual Acuity

Clinical Study Protocol

Johnson & Johnson Vision Care, Inc.

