5.2. Masking

This is a single-masked (partial) study with the subjects being masked. Subjects will be aware that there are differences in modalities between lens types however they will not be told anything regarding the optical design other than the design is intended to correct for their spherical refractive error and presbyopia. Subjects will be unaware of the identity of the assigned investigational products. Investigators and clinical site personnel involved in the data collection will be aware of the identity of the assigned investigational products.

Clinical Study Protocol

Johnson & Johnson Vision Care, Inc.

The identity of the study lenses will be masked to subjects by over labeling the blister packs with a label containing the study number, lot number, sphere power, add power, expiration date and the randomization codes. Investigators and medical monitor will have access to the decode information translating the randomization codes into Test and Control arms.

Under normal circumstances the mask should not be broken until all subjects have completed the study and the database is finalized. Otherwise, the mask should be broken only if specific emergency treatment/course of action would be dictated by knowing the treatment status of the subject. In such cases, the Investigator may, in an emergency, contact the medical monitor. In the event the mask is broken, the Sponsor must be informed as soon as possible. The date, time, and reason for the unmasking must be documented in the subject record. The Investigator is also advised not to reveal the study treatment assignment to the clinical site or Sponsor personnel.

Subjects who have had their treatment assignment unmasked are expected to return for all remaining scheduled evaluations. Subjects who are discontinued may be replaced.

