6. STUDY INTERVENTION

6.1. Identity of Test Articles

The following contact lenses will be used in this study:

Table 1: Test Articles

	Test Lens	Control Lens
Name	JJV Investigational Multifocal Contact Lens	1-Day Acuvue® Moist Brand Multifocal Contact Lens
Manufacturer	Johnson & Johnson® Vision, Inc.	Johnson & Johnson® Vision, Inc.

Clinical Study Protocol
Johnson & Johnson Vision Care, Inc.

	[REDACTED]	
Lens Material	senofilcon A	etafilcon A
Nominal Base Curve	8.35 mm	8.4 mm (labeled)
Nominal Diameter (mm)	14.3 mm	14.3mm
Nominal Distance Powers (D)	+1.00 D to +4.00 D in 0.25 D steps	+1.00 D to +4.00 D in 0.25 D steps
Nominal Cylinder Powers (D) and Axes	None	None
Nominal ADD Powers (D)	Low, Mid, Hgh	Low, Mid, Hgh
Water Content	38%	58%
Center Thickness	0.070 mm (-3.00 D)	0.084 mm (-3.00 D)
Oxygen Permeability (Dk)	122.0	28.0
Wear Schedule in Current Study	Daily Wear Reusable	Daily Wear
Replacement Frequency	Two Weeks	Daily Disposable
Packaging Form (vial, blister, etc.)	Blister	Blister

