10. DEVIATIONS FROM THE PROTOCOL

Investigator will notify study sponsor upon identification of a protocol deviation. Protocol deviations must be reported to the sponsor within 24 hours after discovery of the protocol deviation. The Investigator will report deviations per IRB/IEC requirements. All deviations will be tracked and corrective actions implemented as appropriate.

If it becomes necessary for the Investigator to implement a deviation in order to eliminate an immediate hazard to the trial subject, the Investigator may implement the deviation immediately without notification to the sponsor. Within 24 hours after the implemented deviation, the Investigator must notify and provide the rationale to the Sponsor and, as required, the IEC/IRB.

If the deviation potentially impacts the safety of patient or changes the technical integrity of the study then it must be reported to IEC/IRB. This is a "Major Deviation".

Minor deviations have no substantive effect on patient safety or technical integrity of the study. They are often logistical in nature. The informed consent must also not be contradicted by the deviation.

Protocol waivers are prohibited

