11. STUDY TERMINATION

The occurrence of one or more Unanticipated Serious Adverse Device Effect (USADE), or any SAE where the relationship to study agent cannot be ruled out, may result in stopping further dispensing of test article. In the event of a USADE or SAE, the Sponsor may unmask the treatment regimen for the subject(s) and will discuss this with the Investigator before any further subjects are enrolled.

The Sponsor will determine when a study will be stopped. The Principal Investigator always has the discretion to initiate stopping the study based on patient safety or if information indicates the study's results are compromised.

JJVC reserves the right to terminate the study at any time for any reason. Additionally, the IEC/IRB reserves the right to terminate the study if an unreasonable risk is determined. The study can be terminated by the Principal Investigator at the individual clinical site due to specific clinical observations, if in their opinion, after a discussion with JJVC, it is determined that it would be unwise to continue at the clinical site.

JJVC (and the IEC/IRB and DMC, if applicable) will evaluate all adverse events. If it is determined that an adverse event presents an unreasonable risk, the investigation, or that part of the investigation presenting the risk, will be terminated as soon as possible.

Should the study be terminated (either prematurely or as scheduled), the Investigator will notify the IEC/IRB and Regulatory Authority as required by local regulatory requirements.

Clinical Study Protocol Johnson & Johnson Vision Care, Inc.

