13. ADVERSE EVENTS

13.1. Definitions and Classifications

Adverse Event (AE) – An AE is “any untoward medical occurrence, unintended disease or injury, or untoward clinical signs (including abnormal laboratory findings) in subjects, users or other persons, whether or not related to the investigational medical device.

This definition includes events related to the investigational medical device or the comparator, and to the procedures involved. For users or other persons, this definition is restricted to events related to investigational medical devices¹

An AE includes any condition (including a pre-existing condition) that:

1. Was not present prior to the study, but appeared or reappeared following initiation of the study.
2. Was present prior to the study, but worsened during the study. This would include any condition resulting from concomitant illnesses, reactions to concomitant medications, or progression of disease states.
3. Pregnancy must be documented as an adverse event and must be reported to the clinical monitor and to the Sponsor immediately upon learning of the event.

Serious Adverse Event (SAE) – An SAE is any adverse event that led to any of the following:

- Death
- Serious deterioration in the health of the subject that resulted in any of the following:
- Life-threatening illness or injury
- Permanent or persistent impairment of a body structure or a body function
- Hospitalization or prolongation of patient hospitalization
- Medical or surgical intervention to prevent life-threatening illness or injury or permanent impairment to a body structure or a body function.
- Chronic disease
- Fetal distress, fetal death or a congenital physical or mental impairment of birth defect.

Diagnoses and conditions that are considered Ocular Serious Adverse Events include, but not limited to:

- Microbial Keratitis (MK)
- Iritis (including cells in the anterior chamber)
- Permanent decrease in best spectacle corrected visual acuity equivalent to 2 acuity lines or greater

Clinical Study Protocol

Johnson & Johnson Vision Care, Inc.

- Central Corneal Opacity
- Central Corneal Neovascularization
- Uveitis
- Endophthalmitis
- Hypopyon
- Hyphemia
- Penetration of Bowman's Membrane
- Persistent Epithelial Defect
- Limbal cell Damage leading to Conjunctivalization

Significant Adverse Events – are defined as events that are symptomatic and warrant discontinuation (temporary or permanent) of the contact lens wear

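### After an SAE that cannot be excluded as related, the synopsis requires dispensing to stop while Section 11 only permits it, and nothing says which governs

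*Combined protocol and SAP*

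**What the plan says.** The rule appears in two places.

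- **Synopsis, Study Termination.** One or more UADEs, or an SAE that may be related, leads to a halt: "any SAE where relationship to study agent cannot be ruled out, will result in stopping further dispensing investigational product". The Sponsor Medical Monitor may then unmask, and *may* discuss the matter with the Principal Investigator before enrolment goes on.
- **Section 11, first paragraph.** One or more USADEs, or the same kind of SAE, leads to a possible halt: "any SAE where the relationship to study agent cannot be ruled out, may result in stopping further dispensing of test article". The Sponsor may then unmask, and *will* discuss the matter with the Investigator before enrolment goes on.

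The rest of Section 11 leaves the decision to stop the study to the Sponsor, lets the Principal Investigator initiate stopping, and requires termination of whatever part of the investigation is judged to present an unreasonable risk.

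Section 13.1 defines a UADE and lists the ocular conditions counted as serious, among them "Iritis (including cells in the anterior chamber"). Section 13.2.1 defines the causality categories.

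**The concern.** A stopping rule exists to settle in advance what happens to other subjects when a qualifying event occurs. Here one event is enough, so there is no accumulating count during which the wording could be clarified. A reader of the synopsis would conclude that dispensing stops on the first event. A reader of Section 11 would conclude that someone may decide to stop it. The sponsor, a site, a monitor and an IEC/IRB could each cite the same document for a different answer. What is at stake is the protection of subjects who have not had the event, in the interval between its report and any judgement about risk.

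**Working it through.** No arithmetic applies. The check compares the two texts and then looks for anything that reconciles them.

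| Element | Synopsis, Study Termination | Section 11 | Same? |
|---|---|---|---|
| SAE trigger | Any SAE not excluded as related | Any SAE not excluded as related | Yes |
| Device-effect trigger | One or more UADEs | One or more USADEs | Label differs |
| Effect on dispensing | *will* stop | *may* stop | **No** |
| Unmasking | *may* | *may* | Yes |
| Discussion before further enrolment | *may* | *will* | **No** |

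**1. The SAE branch.** The triggers match almost word for word, so the difference in the verb cannot be explained by a difference in the event. This branch carries the finding alone.

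**2. The device-effect branch.** USADE is in the abbreviation list, separately from UADE, but Section 13.1 defines only UADE. That definition is confined to serious or life-threatening effects and problems, or death. Section 13.4.1 puts the word *Serious* in brackets inside the UADE name. Reading the two as the same event is therefore reasonable, and on that reading this branch has the same split. It remains an inference.

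**3. Is there a reconciling statement?** I found none. The neighbouring synopsis cells on disallowed medications and on procedures send the reader to Sections 9.1 and 7.2. The Study Termination cell has no such reference and reads as a complete rule. Section 11's sentence on the Sponsor's role concerns stopping the study, and its unreasonable-risk clause applies only after that judgement has been made. Neither says whether dispensing stops on the first qualifying event.

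**4. A worked case.** A subject develops iritis, a listed ocular SAE. The investigator rates it *Possibly Related*, which under Section 13.2.1 means that causality has not been excluded. The trigger is met under both texts.
   - Dispensing stops: consistent with the synopsis and with Section 11.
   - Dispensing continues: consistent with Section 11, not with the synopsis.

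**5. The discussion step.** The split runs the other way: Section 11 is the stricter text. Section 13.2 does not fill the gap. It has the investigator and medical monitor categorise events together, which is different from discussing the matter before enrolment resumes.

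**6. Would earlier experience have triggered the rule?** The study summaries in Section 1.5 describe one SAE, dehydration, judged not related. The lens-related events described there (infiltrative events in both eyes of one subject, and one acute red eye) are classed as significant and non-significant respectively, not serious. On those summaries the rule would not have been triggered.

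**The case against.** The strongest case for leaving the text alone has four parts.

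- **The synopsis is only a summary.** That is a common convention, but the protocol text I have does not state it, and this cell does not defer to Section 11.
- **Stopping satisfies both texts.** This is correct. The texts are inconsistent rather than incompatible. They still part company on whether dispensing may continue, which is the choice the rule exists to settle.
- **Other safeguards operate under either wording.** This is also correct: 24-hour reporting of serious events (Sections 13.4 and 13.4.1), withdrawal of affected subjects (Section 8.2) and termination for unreasonable risk (Section 11). They limit the consequence. None says whether dispensing to other subjects stops automatically.
- **No analysis is affected.** This stands in full.

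Three stronger readings are tempting, and the documents do not support them.

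- **A site that keeps dispensing commits a *Major Deviation*.** Section 10 says "If the deviation potentially impacts the safety of patient or changes the technical integrity of the study then it must be reported to IEC/IRB", and adds "Protocol waivers are prohibited". But both stopping rules are written in the passive and do not instruct a site to halt on its own. A halt across sites would ordinarily come through the sponsor. That the synopsis binds the site directly, and that continuing would meet the Section 10 test, are both inferences. No waiver is in question.
- **The two rules halt different lenses.** The synopsis, under Test Article(s), has "Investigational Products: JJV Investigational Multifocal Contact Lens manufactured in senofilcon A material" and lists the Control separately as an approved product, while "Table 1: Test Articles" in Section 6.1 covers both lenses. Section 5.2, however, writes "Subjects will be unaware of the identity of the assigned investigational products", where the plural term appears to cover both assigned lenses. The two terms may be synonyms, so a difference in scope is not demonstrated.
- **The halt is a temporary pause until the sponsor has evaluated the event.** Neither text gives a time limit or a restart condition.

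**Conclusion.** The inconsistency is real and should be corrected. For an SAE that cannot be excluded as related, the same version of the protocol both requires and merely permits a halt in dispensing, and no available text gives precedence. The same holds for the device-effect trigger, on the assumption that UADE and USADE mean the same event. The *may*/*will* difference on discussion before further enrolment is a lesser inconsistency in the same two paragraphs.

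The size is operational, not statistical: no estimate, sample size, power or type I error changes, and the prior studies as summarised would not have triggered the rule. It matters because one event is sufficient and the rule protects subjects. The conclusion rests on the protocol text available for review, from which a few front and end pages had been removed. A precedence statement there would resolve it.

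**What to change.** State one rule, in identical words, in the Study Termination cell of the synopsis and in the first paragraph of Section 11:

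1. Use the defined term UADE in both places.
2. In Section 11, change *may* to *will* for the effect on dispensing. A mandatory stop complies with both current texts.
3. In the synopsis, change *may* to *will* for discussion with the investigator before further enrolment.
4. If the sponsor wants dispensing to be able to resume, for example after its own evaluation of the event, add that condition expressly and say who decides. It would be a new provision that relaxes the synopsis rule.

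If the sponsor in fact intends the halt to be discretionary, the synopsis must change instead. That should be a deliberate choice, because it removes the automatic stop now stated there. While the paragraphs are open, naming the lens or lenses covered would be a useful clarification, though not the correction of a shown error.

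The cost is a wording edit in two places, sent to the IEC/IRB as a protocol revision under Section 18.3. Design, sample size and analysis are untouched.
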